11.2.4 Response Criteria

11.2.4.1 Evaluation of Target Lesions

Complete Response (CR): Disappearance of all target lesions. Any pathological lymph nodes (whether target or non-target) must have reduction in short axis to <10 mm (<1 cm).

Partial Response (PR): At least a 30% decrease in the sum of the diameters of target lesions, taking as reference the baseline sum diameters.

Progressive Disease (PD): At least a 20% increase in the sum of the diameters of target lesions, taking as reference the smallest sum on study (this includes the baseline sum if that is the smallest on study). In addition to the relative increase of 20%, the sum must also demonstrate an absolute increase of at least 5 mm (0.5 cm). (Note: the appearance of one or more new lesions is also considered progressions).

Patients that are clinically well may continue on therapy following RECIST progression with new lesions or increase in target lesions provided the criteria in Section [11.4](#) are met.

Stable Disease (SD): Neither sufficient shrinkage to qualify for PR nor sufficient increase to

qualify for PD, taking as reference the smallest sum diameters while on study.

11.2.4.2 Evaluation of Non-Target Lesions

Complete Response (CR): Disappearance of all non-target lesions and normalization of tumor marker level. All lymph nodes must be non-pathological in size (<10 mm [<1 cm] short axis).

Note: If tumor markers are initially above the upper normal limit, they must normalize for a patient to be considered in complete clinical response.

Non-CR/Non-PD: Persistence of one or more non-target lesion(s) and/or maintenance of tumor marker level above the normal limits.

Progressive Disease (PD): Appearance of one or more new lesions and/or *unequivocal progression* of existing non-target lesions. *Unequivocal progression* should not normally trump target lesion status. It must be representative of overall disease status change, not a single lesion increase.

Although a clear progression of “non-target” lesions only is exceptional, the opinion of the treating physician should prevail in such circumstances, and the progression status should be confirmed at a later time by the review panel (or Principal Investigator).

11.2.4.3 Evaluation of Best Overall Response

The best overall response is the best response recorded from the start of the treatment until disease progression/recurrence (taking as reference for progressive disease the smallest measurements recorded since the treatment started). The patient's best response assignment will depend on the achievement of both measurement and confirmation criteria.

For Patients with Measurable Disease (*i.e.*, Target Disease)

Target Lesions	Non-Target Lesions	New Lesions	Overall Response	Best Overall Response when Confirmation is Required*
CR	CR	No	CR	≥ 4 wks. Confirmation**
CR	Non-CR/Non-PD	No	PR	≥ 4 wks. Confirmation**
CR	Not evaluated	No	PR	
PR	Non-CR/Non-PD/not evaluated	No	PR	
SD	Non-CR/Non-PD/not evaluated	No	SD	Documented at least once ≥ 4 wks. from baseline**
PD	Any	Yes or No	PD	no prior SD, PR or CR
Any	PD***	Yes or No	PD	
Any	Any	Yes	PD	

- * See RECIST 1.1 manuscript for further details on what is evidence of a new lesion.
- ** Only for non-randomized trials with response as primary endpoint.
- *** In exceptional circumstances, unequivocal progression in non-target lesions may be accepted as disease progression.

Note: Patients with a global deterioration of health status requiring discontinuation of treatment without objective evidence of disease progression at that time should be reported as “*symptomatic deterioration*.” Every effort should be made to document the objective progression even after discontinuation of treatment.

For Patients with Non-Measurable Disease (*i.e.*, Non-Target Disease)

Non-Target Lesions	New Lesions	Overall Response
CR	No	CR
Non-CR/non-PD	No	Non-CR/non-PD*
Not all evaluated	No	not evaluated
Unequivocal PD	Yes or No	PD
Any	Yes	PD
* ‘Non-CR/non-PD’ is preferred over ‘stable disease’ for non-target disease since SD is increasingly used as an endpoint for assessment of efficacy in some trials so to assign this category when no lesions can be measured is not advised		

11.2.5 Duration of Response

Duration of overall response: The duration of overall response is measured from the time measurement criteria are met for CR or PR (whichever is first recorded) until the first date that recurrent or progressive disease is objectively documented (taking as reference for progressive disease the smallest measurements recorded since the treatment started).

The duration of overall CR is measured from the time measurement criteria are first met for CR until the first date that progressive disease is objectively documented.

Duration of stable disease: Stable disease is measured from the start of the treatment until the criteria for progression are met, taking as reference the smallest measurements recorded since the treatment started, including the baseline measurements.

11.2.6 Progression-Free Survival

PFS is defined as the duration of time from start of treatment to time of progression or death, whichever occurs first.

11.2.7 Response Review

For trials where the response rate is the primary endpoint, it is strongly recommended that all responses be reviewed by an expert(s) independent of the study at the study’s completion. Simultaneous review of the patients’ files and radiological images is the best approach.

11.3 iRECIST Response Assessment

Overall response will also be assessed using iRECIST as an exploratory endpoint, for comparison to RECIST v1.1.

Immunotherapeutics may result in infiltration of immune cells leading to transient increase in the size in malignant lesions, or undetectable lesions becoming detectable. Investigators should continue treatment, as appropriate, in the absence of unacceptable toxicity, until unequivocal disease progression. This is particularly important for patients in whom pseudoprogression may have occurred. Follow up response assessments must be continued until unequivocal disease progression has occurred.

The iRECIST criteria are identical to those of RECIST 1.1 in many respects but have been adapted to account for instances where an increase in tumor burden, or the appearance of new lesions, does not reflect true tumor progression.

Key differences are described below. All responses defined using iRECIST criteria are designated with a prefix. iRECIST time-point and best overall responses will be recorded separately. Unlike RECIST 1.1, iRECIST requires the confirmation of progression and uses the terms iUPD (unconfirmed progression) and iCPD (confirmed progression). Confirmatory scans should be performed at least 4 weeks, but no longer than 8 weeks after iUPD.

Confirming progression: Unlike RECIST 1.1, iRECIST requires the confirmation of progression and uses the terms iUPD (unconfirmed progression) and iCPD (confirmed progression). Confirmatory scans should be performed at least 4 weeks, but no longer than 8 weeks, after iUPD.

iCPD is confirmed if further increase in tumor burden, compared to the last assessment, is seen as evidenced by one or more of the following:

- Continued increase in tumor burden (from iUPD) where RECIST 1.1 definitions of progression had been met (from nadir) in target, non-target disease, or new lesions.
 - Progression in target disease worsens with an increase of at least 5 mm in the absolute value of the sum.
 - Continued unequivocal progression in non-target disease with an increase in tumor burden.
 - Increase in size of previously identified new lesion(s) (an increase of at least 5 mm in the absolute value of the sum of those considered to be target new lesions) or additional new lesions.
- RECIST 1.1 criteria are met in lesions types (target or non-target or new lesions) where progression was not previously identified, including the appearance of additional new lesions.

If iUPD is not confirmed at the next assessment, then the appropriate response will be assigned (iUPD if the criteria are still met, but no worsening, or iSD, iPR, or iCR if those criteria are met compared to baseline). The prior documentation of iUPD does not preclude assigning iCR, iPR,

or iSD in subsequent time-point assessments or as best overall response (BOR) providing that iCPD is not documented at the next assessment after iUPD (*Lancet Oncol* 18:e143-e152, 2017 - Table 2).

New lesions:

New lesions should be assessed and measured as they appear using RECIST 1.1 criteria (maximum of 5 lesions, no more than 2 per site, at least 10 mm in long axis [or 15 mm in short axis for nodal lesions]), and recorded as New Lesions - Target (NLT) and New Lesion - Non-Target (NLNT) to allow clear differentiation from baseline target and non-target lesions.

New lesions may either meet the criteria of NLT or NLNT to drive iUPD (or iCPD). However, the measurements of target lesions should NOT be included in the sum of measures of original target lesions identified at baseline. Rather, these measurements will be collected on a separate table in the case record form.

PD is confirmed in the New Lesion category if the next imaging assessment, conducted at least 4 weeks (but not more than 8 weeks) after iUPD confirms further progression from iUPD with either an increase of at least 5 mm in the absolute value of the sum of NLT OR an increase (but not necessarily unequivocal increase) in the size of NLNT lesions OR the appearance of additional new lesions.

Time-point (TP) iResponse

Target Lesions*	Non-Target Lesions*	New Lesions*	Time Point Response	
			No prior iUPD**	Prior iUPD**, ***
iCR	iCR	No	iCR	iCR
iCR	Non-iCR/Non-iUPD	No	iPR	iPR
iPR	Non-iCR/Non-iUPD	No	iPR	iPR
iSD	Non-iCR/Non-iUPD	No	iSD	iSD
iUPD with no change OR decrease from last TP	iUPD with no change OR decrease from last TP	Yes	NA	NLs confirms iCPD if NLs were previously identified and increase in size (≥ 5 mm in SOM for NLT or any increase for NLNT) or number. If no change in NLs (size or number) from last TP, remains iUPD.

Time-point (TP) iResponse

Target Lesions*	Non-Target Lesions*	New Lesions*	Time Point Response	
			No prior iUPD**	Prior iUPD**, ***
iSD	iUPD	No	iUPD	Remains iUPD unless iCPD confirmed based in further increase in size of NT disease (need not meet RECIST 1.1 criteria for unequivocal PD).
iUPD	Non-iCR/Non-iUPD	No	iUPD	Remains iUPD unless iCPD confirmed based on further increase in SOM of at least 5 mm, otherwise remains iUPD.
iUPD	iUPD	No	iUPD	Remains iUPD unless iCPD confirmed based on further increase in: 
 • previously identified T lesion iUPD SOM ≥ 5 mm and/or • NT lesion iUPD (prior assessment - need not be unequivocal PD)
iUPD	iUPD	Yes	iUPD	Remains iUPD unless iCPD confirmed based on further increase in: 
 • previously identified T lesion iUPD ≥ 5 mm and/or • previously identified NT lesion iUPD (need not be unequivocal) and/or • size or number of new lesions previously identified
Non-iUPD/PD	Non-iUPD/PD	Yes	iUPD	Remains iUPD unless iCPD confirmed based on increase in size or number of new lesions previously identified.

* Using RECIST 1.1 principles. If no PSPD occurs, RECIST 1.1 and iRECIST categories for CR, PR, and SD would be the same.
 
** in any lesion category.
 
*** previously identified in assessment immediately prior to this TP.
				

All patients will have their iBOR from the start of study treatment until the end of treatment

classified as outlined below.

iRECIST best overall response (iBOR)

TPR 1	TPR 2	TPR 3	TPR 4	TPR 5	iBOR
iCR	iCR, iPR, iUPD, NE	iCR, iPR, iUPD, NE	iUPD	iCPD	iCR
iUPD	iPR, iSD, NE	iCR	iCR, iPR, iSD, iUPD, NE	iCR, iPR, iSD, iUPD, iCPD, NE	iCR
iUPD	iPR	iPR, iSD, iUPD, NE	iPR, iSD, iUPD, NE, iCPD	iPR, iSD, iUPD, NE, iCPD	iPR
iUPD	iSD, NE	PR	iPR, iSD, iUPD, NE	iPR, iSD, iUPD, iCPD, NE	iPR
iUPD	iSD	iSD, iUPD, NE	iSD, iUPD, iCPD, NE	iSD, iUPD, iCPD, NE	iSD
iUPD	iCPD	Anything	Anything	Anything	iCPD
iUPD	iUPD	iCPD	Anything	Anything	iCPD
iUPD	NE	NE	NE	NE	iUPD

Table assumes a randomized study where confirmation of CR or PR is not required.
 
 • NE = not evaluable that cycle. • Designation "I" for BOR can be used to indicate prior iUPD to aid in data interpretation. • For patients with non-target disease only at baseline, only CR or non-CR/non-PD can be assigned at each TPR but is not shown in the table for ease of presentation. 					

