5.4 Duration of Follow-Up

Patients will be followed for 90 days after the last dose of atezolizumab is administered or until the patient enrolls on another protocol or death, whichever comes first. Follow-up will consist of three telephone calls from the Study Team: one call between Day 27 and Day 30 after the last dose of atezolizumab, one call between Day 57 and Day 60 after the last dose, and one call between Day 87 and Day 90 after the last dose. Patients removed from study for unacceptable adverse event(s) will be followed until resolution or stabilization of the adverse event.

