5.5 Criteria for Removal from Treatment and/or Study

Patients will be removed from study for one of the following reasons: completed 30-day follow-up period, toxicities are unresolved but stabilized, patient enrolls on another protocol, patient receives other type of treatment-intent therapy, pregnancy, or death. The reason for study removal and the date the patient was removed must be recorded on the case report form.

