6. DOSING DELAYS/DOSE MODIFICATIONS

6.1 General AE Management and Dose Modification Guidelines

There will be no dose reduction for atezolizumab in this study.

Patients may temporarily suspend study treatment for up to 84 days (12 weeks) beyond the scheduled date of delayed infusion if study drug-related toxicity requiring dose suspension is experienced. If atezolizumab is held because of AEs for >84 days beyond the scheduled date of infusion, the patient will be discontinued from atezolizumab and will be followed for safety and efficacy as specified in this protocol. If the AE resolves within 84 days and the patient is receiving corticosteroid therapy for the event, atezolizumab may be held for longer than 84 days (up to 4 weeks) in order to allow tapering of the steroid dose to ≤ 10 mg oral prednisone or equivalent.

Dose interruptions for reasons other than toxicity, such as surgical procedures, may be allowed. The acceptable length of interruption will be at the discretion of the study PI in consultation with CTEP.

The primary approach to grade 1 to 2 irAEs is supportive and symptomatic care with continued treatment with atezolizumab; for higher-grade irAEs, atezolizumab should be withheld and oral and/or parenteral steroids administered. Recurrent grade 2 irAEs may also mandate withholding atezolizumab or the use of steroids. Assessment of the benefit risk balance should be made by the investigator, with consideration of the totality of information as it pertains to the nature of the toxicity and the degree of clinical benefit a given patient may be experiencing prior to further administration of atezolizumab. Atezolizumab should be permanently discontinued in patients with life threatening irAEs.

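### The planned RECIST 1.1 versus iRECIST comparison (objective 1.3.1) uses two best-response windows that close at different times, and the iRECIST window conflicts with other text in Section 11.3

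*Combined protocol and SAP*

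**What the plan says.** Section 11.2.4.3 defines the RECIST 1.1 window: "The best overall response is the best response recorded from the start of the treatment until disease progression/recurrence". It sets no limit at the end of treatment. The same section adds, for patients who stop because of symptomatic deterioration: "Every effort should be made to document the objective progression even after discontinuation of treatment".

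Section 11.3 defines the iRECIST window differently: "All patients will have their iBOR from the start of study treatment until the end of treatment". The protocol does not say whether the end of treatment means the last dose or the decision to stop. Earlier in Section 11.3 the plan states: "Follow up response assessments must be continued until unequivocal disease progression has occurred". It also asks for a confirmatory scan 4 to 8 weeks after iUPD, without restricting this to patients still on drug. A footnote to the time-point response table says that CR, PR and SD should agree between the two systems when there is no pseudoprogression.

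On imaging after treatment, the text pulls in two directions. Under Section 6.1, when a hold for an adverse event exceeds the allowed limit, "the patient will be discontinued from atezolizumab and will be followed for safety and efficacy as specified in this protocol". The Section 10 calendar marks tumor measurements in the Off Treatment column. Against this, Section 5.4 says: "Follow-up will consist of three telephone calls from the Study Team". Section 5.4 also says "Patients will be followed for 90 days after the last dose of atezolizumab", whereas Section 5.5 takes patients off study at a "completed 30-day follow-up period".

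**The concern.** Objective 1.3.1 asks whether iRECIST classifies these patients differently from RECIST 1.1. The answer is interpretable only if the two classifications draw on the same scans and differ in how they treat progression. With unequal windows, some discordance can arise only because one count stops sooner.

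Two patterns follow from the literal text.

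- (a) A patient stops drug without progression and first reaches a confirmed PR on later scans. RECIST counts the response and iRECIST does not. No pseudoprogression has occurred, so this contradicts the protocol's own footnote.
- (b) A patient stops at iUPD and is rescanned. That scan cannot move the iRECIST best response to iCPD, iSD, iPR or iCR, although Section 11.3 asks for the scan for that purpose.

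The comparison will rest on few discordant patients, so one or two created by the window could change how it reads.

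**Working it through.** **Step 1: apply the two definitions to four courses.**

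| Course | RECIST 1.1 best response | iRECIST best response | Source of any difference |
|---|---|---|---|
| Stable on drug, stops without progression, first PR and its confirmation on later scans | PR | iSD | Window only: pattern (a) |
| First PR on drug, confirming scan after stopping | PR | iPR (the iRECIST table needs no confirmation) | None |
| First assessment is iUPD, drug stopped, rescanned 4 to 8 weeks later | PD, window already closed | iUPD whatever the scan shows | Lost iRECIST information: pattern (b) |
| Continues past RECIST progression under Section 11.4, rescanned on drug | PD, window already closed | Updated by the scan | Intended difference |

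In pattern (b) the later scan counts toward best response under neither criterion. If it shows iCPD, the patient is a non-responder either way. The response classification is affected only if the scan shows shrinkage.

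**Step 2: size of pattern (a).** The plan gives no figure for this comparison, so there is nothing to reproduce. Inputs:

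- N = 17 evaluable adults per cohort at most (Section 13.1), so 3 × 17 = 51 at most.
- q = share who stop drug without RECIST progression. Not in the documents. Assumed 5% to 13.7%, then 5% to 20%. The 13.7% is the rate of treatment-related grade 3 or 4 adverse events in Section 2.3.4.3. It is not a discontinuation rate and serves only as a rough upper figure.
- r = share of those who first qualify as responders on scans after stopping. Not in the documents. Assumed 10% to 25%, then 5% to 25%.

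Expected RECIST-only responders = N × q × r.

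- Narrow range: 51 × 0.05 × 0.10 = 0.26, to 51 × 0.137 × 0.25 = 1.75.
- Wide range: 51 × 0.05 × 0.05 = 0.13, to 51 × 0.20 × 0.25 = 2.55.
- Per cohort, wide range: 17 × 0.0025 = 0.04, to 17 × 0.05 = 0.85.
- Chance of at least one in a full cohort, 1 − (1 − qr)^17: 1 − 0.9975^17 = 4%, to 1 − 0.95^17 = 58%.
- One such patient moves a 17-patient cohort's response rate by 1/17 = 5.9 percentage points.

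The upper ends are generous. They require all three cohorts to pass stage one. Under the Simon rule, each cohort stops at 9 with probability .63 if the true response rate is 5% (stated in Section 13.1 and reproduced as 0.630), and with probability 0.075 if it is 25%. All three therefore reach stage two with probability (1 − 0.630)^3 = 0.05 or (1 − 0.075)^3 = 0.79. The upper ends also make no separate allowance for the small number of scheduled off-treatment scans or for the second scan that RECIST confirmation needs.

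**Step 3: direction.** Three forces act on the difference in response rates.

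- The shorter iRECIST window lowers the iRECIST rate.
- The iRECIST best-response table assumes a randomized study without confirmation of CR or PR. Section 11.2.4.3 requires confirmation at 4 weeks or more when a non-randomized trial has response as its primary endpoint, as here. This raises the iRECIST rate.
- Responses after RECIST progression count only under iRECIST, by design. This also raises the iRECIST rate.

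The documents do not allow these to be netted out.

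**The case against.** The strongest reply is that the mismatch has little to act on. Section 5.4 makes post-treatment follow-up a set of telephone calls, and Section 5.5 ends study participation at 30 days. The efficacy follow-up in Section 6.1 is only what the protocol specifies, and no serial off-treatment imaging is specified. The calendar's off-treatment mark is one column, not a series. Pattern (a) needs two scans off drug at least 4 weeks apart. The main route for pseudoprogression is continued treatment under Section 11.4, where the 4 to 8 week scan falls inside the iRECIST window. Time-point responses are recorded separately from best response, so a scan that is taken is not lost from the data. The objective is exploratory, with no test or decision rule, and Section 13.3 promises caveats.

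All of this stands, and it limits the size. It does not remove the conflict: Section 11.3 calls for scans that its own best-response rule then sets aside.

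Three stronger readings are tempting, and the documents do not support them. A reader might infer that every scan after stopping drug counts under one criterion only. That holds for pattern (a), not for pattern (b). A reader might infer that pseudoprogression is hidden in every patient who stops at first RECIST progression. Only those actually rescanned after stopping are affected, and patients who continue are rescanned on drug. A reader might infer that the comparison is biased against iRECIST. Step 3 shows opposing forces and no established net direction.

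**Conclusion.** The two windows differ as written, and the iRECIST one conflicts with the assessment and rescanning requirements in Section 11.3. The comparison in objective 1.3.1 would then mix a difference in progression rule with a difference in when counting stops. Pattern (a) probably touches roughly 0 to 2 of up to 51 adults. This rests on assumed rates of stopping and of late response; the 2.55 at the corner of the wide range takes the highest value of both. The number in pattern (b) cannot be estimated, because the documents do not say how often patients who stop at iUPD are rescanned. The primary response rate and the Simon decision rule use RECIST 1.1 only and are unaffected. The change is still worth making, because the objective is planned, discordant patients will be few, and the correction costs almost nothing.

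**What to change.** 1. In Section 11.3, replace the end-of-treatment limit on iRECIST best response with: *until iCPD, start of another anti-cancer therapy, or last tumor assessment, whichever is first, including scans after the last dose*. A scan taken 4 to 8 weeks after stopping at iUPD then counts.
2. In Section 11.2.4.3, add the same outer limit (new anti-cancer therapy or last tumor assessment) to RECIST best response. New therapy already limits the time frames for duration of response and PFS in Section 1.2.
3. For the comparison, apply the same confirmation rule for CR and PR (4 weeks or more) to both criteria. Without this, aligning the windows would still leave a second difference unrelated to progression.
4. Reconcile the 90-day and 30-day follow-up statements in Sections 5.4 and 5.5, so that it is clear which off-treatment scans can be on study.

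No new scans are needed. The cost is a few sentences and a few more time points to classify. The iRECIST response rate may be slightly lower once confirmation is required.

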1. OBJECTIVES

1.1 Primary Objectives

- 1.1.1 Determine the objective response rates (ORR) using RECIST v 1.1 of atezolizumab in adult (≥ 18 years) patients with CCS and CS

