1.3 Exploratory Objectives

- 1.3.1 Compare RECIST v1.1 vs immune RECIST (iRECIST) in patients with CCS and CS on atezolizumab
- 1.3.2 Examine changes in PD-1/PD-L1 expression in the tumor microenvironment before and after atezolizumab treatment, and correlate treatment-induced changes with clinical response
- 1.3.3 Evaluate potential associations between atezolizumab activity and tumor genomic alterations

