5. TREATMENT PLAN

This is a multicenter open-label phase 2 trial evaluating atezolizumab in adult subjects ≥ 18 years of age and in pediatric/adolescent subjects ≥ 2 years of age with advanced CCS or CS. Patients will be divided into cohorts based on histology upon enrollment. There will be three cohorts: histologically confirmed CCS (or EWSR1 translocation), conventional CS (grade 2 or 3), and dedifferentiated CS.

Patient evaluations will be performed throughout the study as described below. Baseline history, physical examination, laboratory evaluations, urinalysis, and EKG are to be conducted within 8 days prior to the start of protocol therapy. If protocol therapy is started within 8 days of these eligibility screening evaluations (see Section [3.3](#)), values from the screening evaluations may be used as baseline measurements; if >8 days have passed since the screening evaluations, the medical history, physical examination, laboratory evaluations, urinalysis, and EKG must be repeated prior to starting protocol therapy. Baseline imaging scans and ECHO must be done within 28 days prior to the start of protocol therapy.

History and physical examination will be done within 8 days of Day 1 of all cycles. Labs (serum chemistries and CBC with differential) will be performed at baseline as described above, on Cycle 1 Day 15 [± 1 day], and then up to 3 days before the start of each subsequent cycle (LDH and protein do not need to be checked again after baseline). TSH will be checked at baseline (within 8 days of Cycle 1 Day 1) and then up to 3 days before the start of each subsequent cycle. EKG will be repeated as clinically indicated after the baseline measurement described above.

Patients will have a CT scan at baseline (within 28 days prior to start of protocol therapy). Patients will undergo a CT scan and be re-evaluated for response at the end of Cycle 3 and every two cycles thereafter (every 3 cycles for patients on study for >1 year; every 4 cycles for patients on study for >2 years). Given the concern of pseudoprogression ("tumor flare"), patients that are clinically well may continue on therapy following RECIST progression if they meet the criteria outlined in Section 11.4.

Research biopsies (mandatory for adult patients at all sites) and blood samples for PD studies (mandatory for patients ≥ 12 years of age) will be collected as described in Section [9.2](#) and Section [9.3](#).

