11. MEASUREMENT OF EFFECT

11.1 Antitumor Effect – Solid Tumors

Patients should be re-evaluated for response at the end of Cycle 3 (before Cycle 4), and at the end of every two cycles thereafter (before every even-numbered cycle). Restaging scans may be performed less frequently for patients on study for more than 1 year (every three cycles for patients on study for more than 1 year; every four cycles for patients on study more than 2 years). Confirmatory scans should also be obtained ≥ 4 weeks following initial documentation of objective response.

Response and progression will be evaluated in this study using the international criteria proposed by the revised Response Evaluation Criteria in Solid Tumors (RECIST) guideline (version 1.1) [59]. Changes in the largest diameter (unidimensional measurement) of the tumor lesions and the shortest diameter in the case of malignant lymph nodes are used in the RECIST criteria.

Patients that are clinically well may continue on therapy following RECIST progression with new lesions or increase in target lesions, provided the criteria in Section [11.4](#) are met.

Response will also be explored using iRECIST (see Section [11.3](#)). Increasing clinical experience indicates that traditional response criteria such as RECIST may not be sufficient to fully characterize activity in the new era of target therapies and/or biologics. In studies with therapeutic antibodies, complete response, partial response, or stable disease has been shown to occur after an increase in tumor burden, characterized by progressive disease by traditional response criteria. Therefore, conventional response criteria may not adequately assess the activity of immunotherapeutic agents because progressive disease (by initial radiographic evaluation) does not necessarily reflect therapeutic failure. Long-term effect on the target disease must also be captured. The iRECIST criteria, by incorporating specific response patterns

that have been observed with immunotherapeutic agents, have been developed to address these issues and provide standardized response criteria for use with immunotherapy [60].

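### The iRECIST best-response table drops the response confirmation that RECIST 1.1 requires in this trial, so the exploratory RECIST versus iRECIST comparison can show an excess unrelated to pseudoprogression

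*Combined protocol and SAP*

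**What the plan says.** **RECIST 1.1.** Section 11.2.4.3 states: "The patient's best response assignment will depend on the achievement of both measurement and confirmation criteria". Its table asks for confirmation of CR and PR at 4 weeks or more, and a footnote limits this: "Only for non-randomized trials with response as primary endpoint". This trial meets that condition. Section 5 describes it thus: "This is a multicenter open-label phase 2 trial evaluating atezolizumab in adult subjects" patients and pediatric patients, in cohorts set by histology and without randomization. The primary objective in Section 1.1 begins: "Determine the objective response rates (ORR) using RECIST v 1.1 of atezolizumab in adult". Section 11.1 adds: "Confirmatory scans should also be obtained ≥ 4 weeks following initial documentation of objective response".

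**iRECIST.** Section 11.3 says "All patients will have their iBOR from the start of study treatment until the end of treatment" classified by the table that follows it. The footnote to that table reads "Table assumes a randomized study where confirmation of CR or PR is not required". The only confirmation that Section 11.3 describes is of progression (iUPD to iCPD). Nothing there or elsewhere expressly requires an iCR or iPR to be confirmed.

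**The comparison.** Exploratory objective 1.3.1 is to "Compare RECIST v1.1 vs immune RECIST (iRECIST) in patients with CCS and CS on atezolizumab". Section 13 gives no estimand or method for it.

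**The concern.** The comparison is of interest because some patients may respond after apparent progression. RECIST 1.1 scores these patients as progressed, while iRECIST can still credit the response. For a difference between the two criteria to carry that meaning, they should differ only in how they treat progression and new lesions. As written, they also differ on whether a response must be seen twice. A patient with one CR or PR and no confirming scan is then discordant without any pseudoprogression. With few responders expected per cohort, one or two such patients could be a large part of any observed difference.

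**Working it through.** **1. The plan's own figures.** The plan gives no figure for this comparison. The design figures in Section 13.1 (stop at 0/9, positive at 3 or more of 17) were checked with exact binomial probabilities. Early stopping at a 5% response rate is 0.95^9 = 0.630 (plan: at least .63). The probability of a negative result at 5% is 0.953 (plan: at least .95). Power at 25% is 0.812 (plan: at least 81%). All three reproduce. They concern RECIST 1.1 response and do not depend on the iBOR table.

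**2. The iBOR rows that can give a response.**

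| Row | First time point | Later time points | iBOR | RECIST 1.1 |
|---|---|---|---|---|
| 1 | iCR | may be iUPD or not evaluable throughout | iCR | CR not confirmed |
| 2 | iUPD | iCR at the third | iCR | already PD |
| 3 | iUPD | iPR at the second | iPR | already PD |
| 4 | iUPD | PR at the third | iPR | already PD |

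Only row 1 shows the artefact directly. In rows 2–4 RECIST 1.1 progression comes first, and best response under 11.2.4.3 runs only until progression. Discordance there is the signal the comparison looks for. A first iPR with no prior iUPD has no row, so its treatment rests on the footnote.

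**3. Direction.** Take all sequences of CR, PR or SD over one to five scans without progression: 3 + 9 + 27 + 81 + 243 = 363. Score iRECIST as any CR or PR (the footnote's assumption) and RECIST 1.1 as CR or PR at two scans. Scheduled scans in year 1 are two 21-day cycles apart, or 6 weeks, so the 4-week minimum is met. Sequences with exactly one response number 2 × L for L scans, so 2 × (1 + 2 + 3 + 4 + 5) = 30 are responses under iRECIST only. None is a response under RECIST 1.1 only. The mismatch can only raise the iRECIST rate.

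**4. Size.** Inputs are n = 17 adults per cohort and response rates p of 5% and 25% (both Section 13.1), with p read as the rate of first-documented response. The share u of first responses that do not confirm is not in the documents and is assumed to be 10–30%.

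- One unconfirmed response: 1/17 = 5.9 points. At the three-responder threshold this moves 3/17 = 17.6% to 4/17 = 23.5%.
- Expected number: n × p × u.
- p = 5%: 17 × 0.05 = 0.85 first responders; × 0.10 to 0.30 = 0.085 to 0.255, about 0.1–0.3 patients.
- p = 25%: 17 × 0.25 = 4.25; × 0.10 to 0.30 = 0.425 to 1.275, about 0.4–1.3 patients.
- u = 0: zero in both cases.

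If 5% and 25% are instead read as confirmed rates, the excess is n × p × u/(1 − u): 0.09–0.36 patients at 5% and 0.47–1.82 at 25%.

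**The case against.** **A softer reading of the footnote.** The footnote says what the table assumes and may be carried-over text. Section 11.3 describes iRECIST as matching RECIST 1.1 in many respects, and its key differences do not include dropping response confirmation. The request in 11.1 for confirmatory scans is not limited to RECIST 1.1. A footnote to the time-point table says that CR, PR and SD agree when there is no pseudoprogression. This shows that confirmation may have been intended. It does not settle the matter, because 11.3 directs that every patient be classified by the table, and a programmer following it would build in the mismatch. The agreement footnote holds for time-point response but fails for best overall response as written.

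**Which rows are affected.** A reader might infer that the iPR rows also show unconfirmed responses being credited in patients without progression. They do not, since each begins with iUPD. This objection stands and limits the point to row 1 and to the unlisted first iPR.

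**Scope.** The objective is exploratory, Section 13.3 promises caveats on exploratory results, and no iRECIST response rate is defined. Time-point and best responses are recorded separately, so confirmed and unconfirmed iRECIST response can both be derived later. Objective 1.3.1 is not limited to adults, so the denominator may not be 17. All of this stands. It lowers the stakes, but it does not supply a rule, and choosing one after the discordant patients are known would be post hoc.

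**Conclusion.** The plan applies a confirmation rule to RECIST 1.1 response and a no-confirmation table to iRECIST response, then compares the two. Followed as written, part of any iRECIST excess can be unconfirmed first responses and not response after apparent progression. The direction follows from the rules; the size depends on a non-confirmation rate that the documents do not give and may be zero.

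Two stronger conclusions are tempting. One is that a higher iRECIST rate would itself show bias. It would not, because iRECIST allows iCR or iPR after iUPD, so some excess is expected and legitimate. The other is that the trial's efficacy conclusion is at risk. It is not, because the primary response rate, the futility stop and the three-responder rule all use RECIST 1.1. Nor should the size be judged only at the 25% response rate: at 5% the expected number is well below one patient per cohort. This should be corrected before analysis, but it bears on one exploratory objective.

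**What to change.** In Section 11.3, require the confirmation of 11.2.4.3 (4 weeks or more) for iCR and iPR when iBOR is assigned. Replace the randomized-study footnote with a statement of that rule. Adapt the iBOR rows so that a response needs a confirming time point, and add a row for a first iPR without prior iUPD. Unconfirmed responses may also be reported, provided that this is done under both criteria.

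The cost is a table edit and a programming rule. Section 11.1 already plans confirmatory scans after a first response, so no new visits are needed for these cases.
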